5.2.1 TENS Unit, Electrode Placement and Settings

The nursing team will be provided with official training on the appropriate use of TENS unit, prior to its implementation. The nurse taking care of the participant will place the electrodes and manage the TENS unit. An iStim EV804 TENS unit along with 4 AUVON TENS self-adhering stimulating electrodes will be used for each participant.

[figure not shown]

Figure 1: Electrode Placement
Lisón et al (2017). Pain Relief During Office Hysteroscopy. Obstet Gynecol

Electrode Placement: Two sets of two self-adhesive electrodes to be placed parallel to the spinal cord at the T10–L1 and S2–S4 levels as shown in Figure 1.

Activated TENS Output Parameters: Based on randomization the TENS unit will be either activated or left inactive (after a brief initial activation to avoid the unblinding of the participant) 5 minutes prior to and for the duration of the cystoscopic injection procedure. Active parameters are: asymmetric, balanced, biphasic square waveform at a mixed

stimulating frequency that randomly varying between 80 and 100 Hz and a pulse duration of 300 microseconds.

5.3 Masking/Blinding

Participants in both arms of the study will be blinded to whether they received Active TENS unit or Sham TENS unit. Only the nursing team will be notified about the randomization. The care providers performing the procedure and the study coordinator will not be notified about the randomization. The study coordinator will ask the participant and the provider separately (in the absence of the other) whether they felt the participant was in the Active TENS group versus the Sham TENS group at the end of the procedure.

Schedule of Events		
Study Activity	Visit 1 Outpatient Clinic	Visit 2 Outpatient Procedure Cystoscopic Onabotulinum Toxin A Injection
Screening and Informed Consent	X	
Depression and Anxiety Screen		X
Randomization		X
Numerical Pain Score assessment		X
Participant Satisfaction Assessment		X
Participant and Provider Perception regarding Arm of study		X

6 Statistical Plan

6.1 *Sample Size Determination:*

Based on our baseline preliminary data and the study ‘Transcutaneous Nerve Stimulation for Pain Relief During Office Hysteroscopy’ by Lison et al (2017)[6], power calculations were performed. As estimates of the mean and variance of the pain scale we used table 2 from the Lison et al (2017) study and our preliminary data. Group sample sizes of 27 and 27 achieve 80.53% power to reject the null hypothesis of equal means when the population mean difference is $\mu_1 - \mu_2 = 4.0 - 2.0 = 2.0$ with standard deviations of 2.0 for group 1 and 3 for group 2, and with a significance level (alpha) of 0.050 using a two-sided two-sample unequal-variance t-test. With a 10% possible dropout rate, we plan to have 30 participants in each of the study.

6.2 *Statistical Methods:*

6.2.1 **Specific Aim #1: To assess whether the TENS units is effective for intraoperative pain management during office cystoscopic Intradetrusor Onabotulinumtoxin A in women with OAB.**

We plan to compare participant reported pain using a 0-10 numerical pain scale at baseline, during and after cystoscopic intradetrusor onabotulinumtoxin A injection in participants randomized to active TENS units and placebo TENS units. We will compare the change in numerical pain scale from baseline to intraoperatively and intraoperatively to postoperatively between both groups.

Hypothesis: We hypothesize that there will be a clinically significant pain reduction in the Active TENS group.

Interpretation: Assuming that pain as measured is decreased in the Active TENS group when compared to the placebo TENS group, then we will accept our hypothesis. If not, we will perform a subgroup analysis of our data to see if certain groups of people that have better pain reduction with the Active TENS unit and an analysis of risk factors that might contribute to pain with Intradetrusor Onabotulinumtoxin A injection.

Power Calculation: Based on our baseline preliminary data and the study ‘Transcutaneous Nerve Stimulation for Pain Relief During Office Hysteroscopy’ by Lison et al (2017)(6), power calculations were performed. As estimates of the mean and variance of the pain scale we used table 2 from the Lison et al (2017) study and our preliminary data. Group sample sizes of 27 and 27 achieve 80.53% power to reject the null hypothesis of equal means when the population mean difference is $\mu_1 - \mu_2 = 4.0 - 2.0 = 2.0$ with standard deviations of 2.0 for group 1 and 3 for group 2, and with a significance level (alpha) of 0.050 using a two-sided two-sample unequal-variance t-test.

Data Analysis: The data will be analyzed using an intention-to-treat approach. In order to account for individual participant pain sensitivity profiles through the experiment, random effect longitudinal model will be adjusted to the data controlling by treatment and selected covariates at baseline.

6.2.2 Specific Aim # 2: To evaluate the effect of TENS units on participant satisfaction following cystoscopic intradetrusor onabotulinumtoxin A injection in women with OAB.

We plan to evaluate participant satisfaction on a 10 point Likert scale immediately after the procedure in participants randomized to activated TENS units and placebo TENS units.

Hypothesis: There will be a high level of participant satisfaction on a 10 point Likert scale in the active TENS group.

Interpretation: Assuming that the participant satisfaction as measured is high in the Active TENS group, then we will accept our hypothesis. If not, we plan to do a subgroup analysis to see if there are factors that contribute to higher participant satisfaction in certain groups of people in both the Active TENS and Placebo TENS group.

Data Analysis: The data will be analyzed using an intention-to-treat approach. Baseline differences between both groups will be analyzed using Cochran-Mantel-Haenszel test with an Alpha level of 0.05. Spearman rank correlation coefficients between Likert scales will be using to assess the strength of the relationship.

7 Safety and Adverse Events

7.1 *Definitions*

Unanticipated Problems Involving Risk to Subjects or Others (UPIRTSO)

Any unanticipated problem or adverse event that meets the following three criteria:

- Serious: Serious problems or events that results in significant harm, (which may be physical, psychological, financial, social, economic, or legal) or increased risk for the subject or others (including individuals who are not research subjects). These include: (1) death; (2) life threatening adverse experience; (3) hospitalization - inpatient, new, or prolonged; (4) disability/incapacity - persistent or significant; (5) birth defect/anomaly; (6) breach of confidentiality and (7) other problems, events, or new information (i.e. publications, DSMB reports, interim findings, product labeling change) that in the opinion of the local investigator may adversely affect the rights, safety, or welfare of the subjects or others, or substantially compromise the research data, **AND**
- Unanticipated: (i.e. unexpected) problems or events are those that are not already described as potential risks in the protocol, consent document, not listed in the Investigator's Brochure, or not part of an underlying disease. A problem or event is "unanticipated" when it was unforeseeable at the time of its occurrence. A problem or event is "unanticipated" when it occurs at an increased frequency or at an increased severity than expected, **AND**
- Related: A problem or event is "related" if it is possibly related to the research procedures.

Adverse Event

An untoward or undesirable experience associated with the use of a medical product (i.e. drug, device, biologic) in a patient or research subject.

Serious Adverse Event

Adverse events are classified as serious or non-serious. Serious problems/events can be well defined and include:

- death
- life threatening adverse experience
- hospitalization
- inpatient, new, or prolonged; disability/incapacity
- persistent or significant disability or incapacity

And/or per protocol may be problems/events that in the opinion of the sponsor-investigator may have adversely affected the rights, safety, or welfare of the subjects or others, or substantially compromised the research data.

Other important medical events are those that may not be immediately life threatening, but are clearly of major clinical significance include:

- Burns
- Skin Irritation
- Muscle Pain or Soreness

All adverse events that do not meet any of the criteria for serious, should be regarded as **non-serious adverse events**.

Adverse Event Reporting Period

For this study, the study treatment follow-up period is defined as from enrollment to 1 week after receiving the cystoscopic Onabotulinum Toxin A injection.

Preexisting Condition

A preexisting condition is one that is present at the start of the study. A preexisting condition should be recorded as an adverse event if the frequency, intensity, or the character of the condition worsens during the study period.

General Physical Examination Findings

At screening, any clinically significant abnormality should be recorded as a preexisting condition. At the end of the study, any new clinically significant findings/abnormalities that meet the definition of an adverse event must also be recorded and documented as an adverse event.

Post-study Adverse Event

All unresolved adverse events should be followed by the sponsor-investigator until the events are resolved, the subject is lost to follow-up, or the adverse event is otherwise explained. At the last scheduled visit, the sponsor-investigator should instruct each subject to report, to the sponsor-investigator, any subsequent event(s) that the subject, or the subject's personal physician, believes might reasonably be related to participation in this study.

Abnormal Laboratory Values

No abnormal laboratory values are related to the administration of the TENS Unit

Hospitalization, Prolonged Hospitalization or Surgery

Any adverse event that results in hospitalization or prolonged hospitalization should be documented and reported as a serious adverse event unless specifically instructed otherwise in this protocol. Any condition responsible for surgery should be documented as an adverse event if the condition meets the criteria for an adverse event.

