3.5 Primary endpoints

- Numeric Analog Pain Score (0-10) at Baseline before Office Cystoscopic Onabotulinum Toxin A injection (collected after the participant changes into procedural gown)
- Numeric Analog Pain Score (0-10) during Office Cystoscopic Onabotulinum Toxin A injection (collected during middle of the procedure, after the 10th injection)
- Numeric Analog Pain Score (0-10) after Office Cystoscopic Onabotulinum Toxin A injection (collected 5-10 minutes after the procedure)

Source: The Numerical Analog Pain Score will be documented by the study coordinator into the case report forms and later transferred in the Red Caps Data Management system.

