Participants will be randomized to two groups using a computerized sequence generator based on permuted block randomization (1:1 allocation ratio) on the day of the procedure by the registered nurse (RN) taking care of the participant. Participants in Group 1 will receive an Activated TENS unit for pain control. Participants in Group 2 will have a Sham, inactive TENS unit for pain control. Both groups will be blinded to the type of TENS unit received. The nursing team taking care of the participant will know about the randomization. The care providers performing the procedure and the study coordinator will not be notified about the randomization.

On the day of the procedure, after baseline questionnaires and randomization, the participant will receive intraurethral lidocaine jelly as part of the standard pain control measures. Her bladder is then emptied using a Foley Catheter, and at the same time the bladder is then backfilled with 30 ml (300 mg/30 ml) of 1 % plain lidocaine solution. A waiting period of 30-50 minutes duration is allowed for the intravesicle lidocaine to take effect. During this wait period, participant is asked to lie supine for 10-15 minutes, then roll to the left side for 10-15 minutes and then to right side for about 10-15 minutes.

The participant, the provider taking care of the participant and the study coordinator assigned to the study will be blinded to the randomization. Both groups of participants will receive the TENS unit electrode placement during this wait period by the RN.

In participants randomized to the Active TENS group, the TENS unit will be initiated on standard setting (see ‘TENS, Electrode Placement, and Settings’) 5 minutes before starting the cystoscopy and will last the duration of the cystoscopy. The device intensity (amplitude) will be individually adjusted to each participant’s maximum sensory level, which is the strongest reported tingling feeling without pain and muscle contractions and kept at this setting for the duration of the procedure.

Participants randomized to the Sham TENS group will not receive the TENS therapy. Instead, they will receive electrode placement followed by initiation of the TENS unit until the participant feels the tingling sensation, following which the TENS unit will be immediately turned off by the RN. The participant will be notified by the RN that the TENS stimulus has been turned down such that they are not able to feel the tingling sensation anymore.

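### Aim 1 lists the intraoperative-to-postoperative pain change without a role, although it measures persistence or recovery and cannot be read alone as evidence for or against TENS efficacy

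*Combined protocol and SAP*

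**What the plan says.** Sections 2.1 and 6.2.1 both describe the Aim 1 comparison in the same sentence: "We will compare the change in numerical pain scale from baseline to intraoperatively and intraoperatively to postoperatively between both groups". Neither section ranks the two changes or gives the second an expected direction or a descriptive role. Section 6.2.1 also plans a comparison of the scores themselves: "We plan to compare participant reported pain using a 0-10 numerical pain scale at baseline, during and after cystoscopic intradetrusor onabotulinumtoxin A injection".

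Section 3.5 lists all three pain scores as primary endpoints. The intraoperative score is "collected during middle of the procedure, after the 10th injection" and the last score is "collected 5-10 minutes after the procedure". Section 5.2 starts active TENS "5 minutes before starting the cystoscopy and will last the duration of the cystoscopy", and Section 5.2.1 gives the same window: "5 minutes prior to and for the duration of the cystoscopic injection procedure". The intraoperative score is therefore taken under stimulation, and the last score after planned stimulation has ended.

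The hypothesis in Section 6.2.1 predicts less pain with active TENS but names no time points. The interpretation paragraph accepts the hypothesis if measured pain is lower with active than with placebo TENS, again without a time point. The planned longitudinal model with random effects names no arm-by-time term and no primary contrast.

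**The concern.** Aim 1 asks whether TENS helps with pain during the procedure. The baseline-to-intraoperative change addresses that, because its starting score precedes stimulation. The intraoperative-to-postoperative change does not: its starting score is itself affected by treatment. If TENS lowers mid-procedure pain, the active arm has less far to fall afterwards, so the benefit enters this contrast with its sign reversed.

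At stake is how the results are read. A report could show two co-listed Aim 1 changes, both significant and pointing in opposite directions, with nothing in the plan on how to reconcile them. The wording of the hypothesis adds to the risk, because a reduction in pain with no time points named could be taken to mean the fall from mid-procedure to afterwards.

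**Working it through.** **1. The plan's own figure.** Section 6.1 uses 27 per arm, a difference of 4.0 - 2.0 = 2.0, two-sided alpha 0.05 and an unequal-variance t-test, "with standard deviations of 2.0 for group 1 and 3 for group 2".
- SE = sqrt(2²/27 + 3²/27) = 0.694; 2.0/0.694 = 2.88; Satterthwaite df = 45.3.
- Noncentral-t power = 80.53%, as stated. Dropout: 27/0.90 = 30 per arm, as stated.

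**2. What the second contrast estimates.** Let D be the active minus sham mean at a given time.

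(post_active - intra_active) - (post_sham - intra_sham) = D_post - D_intra

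Place the plan's 2-point benefit mid-procedure (D_intra = -2) and let r be the share still present at the last score (D_post = -2r). The contrast is then 2(1 - r), and a positive value means a larger fall in sham:
- r = 0: +2.0
- r = 0.5: +1.0
- r = 1: 0
- r = 1.25: -0.5, the only one of these four cases that favours TENS

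**3. How often it would be significant.** Section 6.1 ties its means and SDs to no time point and to no named arm. Section 5.2 gives the numbering: "Participants in Group 1 will receive an Activated TENS unit for pain control". The assumptions, which are not in the documents, are:
- the 2-point difference and the SDs apply mid-procedure, with sham the higher at 4.0;
- post-procedure SDs run from 1.5 in both arms up to the plan's 2 and 3;
- the within-person correlation is 0.2-0.5;
- 27 per arm are analysed.

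Change SD per arm = sqrt(SDi² + SDp² - 2·rho·SDi·SDp), where SDi and SDp are the intraoperative and post-procedure SDs.
- Least favourable corner (post SDs 2 and 3, rho 0.2): change SDs 2.53 and 3.79, SE 0.878.
- Most favourable corner (post SD 1.5 in both arms, rho 0.5): change SDs 1.80 and 2.60, SE 0.609.

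| Share retained | Contrast | Chance of a significantly larger fall in sham |
|---|---|---|
| None | 2.0 | 61-90% |
| A quarter | 1.5 | 39-67% |
| Half | 1.0 | 20-36% |
| Three quarters | 0.5 | 8-12% |
| All | 0 | 2.5% |

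The chance of significance in favour of TENS is at most about 0.1% at half retained and 2.5% at full retention. A random-intercept model with an arm-by-time term gives similar figures for a larger fall in sham: 66-94%, 24-46% and 3-5% for none, half and all retained.

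**4. Both changes significant in one trial, in opposite directions.** This was simulated with 20,000 trials per setting, baseline SD 1-2 and a common correlation of 0.2-0.5. The baseline-to-intraoperative change favours TENS and the later change shows a larger fall in sham in 50-85% of trials if none is retained, 19-36% if half and 2-3% if all.

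**5. The replacement comparisons.** With the same mid-procedure inputs and baseline SD 1-2:
- Baseline-to-intraoperative change: power is 70% (baseline SD 2, rho 0.2; change SDs 2.53 and 3.26) to 90% (baseline SD 1.5, rho 0.5; change SDs 1.80 and 2.60).
- Intraoperative score adjusted for baseline: the SDs are multiplied by sqrt(1 - rho²). At rho 0.2 they are 1.96 and 2.94, power 82%. At rho 0.5 they are 1.73 and 2.60, power 90%.
- Post-procedure score adjusted for baseline: power is 30-79% if half the benefit is retained and at least 82% if all is.

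**The case against.** The contrast answers a fair question, namely whether the between-arm difference lasts once stimulation stops. The plan also compares pain during and after the procedure, so a reader with all three means can see that a smaller rise followed by a smaller fall is one coherent pattern of benefit and then fading. The interpretation paragraph most naturally means lower pain between arms, not a larger fall. Naming one primary time point would largely settle the matter.

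Much of this stands, and it rules out three stronger readings that a reader might draw:
- **That the contrast cannot show a benefit at all.** If post-procedure means are equal, it mirrors the intraoperative benefit with reversed sign. It needs the time-specific means to be interpreted.
- **That a significant result in this direction is evidence for sham.** It means only that sham fell further from a higher mid-procedure score.
- **That the trial could reach a wrong conclusion by rule.** Section 6.2.1 attaches no decision to this contrast.

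The size is also open. The retained share drives it, and the documents neither give nor bound that share. The correlation range is a choice too: with none retained, a correlation of 0 gives 51-68% and 0.7 gives 95-97%.

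What remains is that the plan lists a contrast that starts from an on-treatment score beside one that starts from baseline, under an aim it does not address, with no guidance on reading it.

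**Conclusion.** The point holds in limited form, with minor to moderate severity. The intraoperative-to-postoperative change measures persistence or recovery and should not be read alone as evidence for or against efficacy. That follows from algebra and from the timing in Sections 3.5, 5.2 and 5.2.1, and needs no assumption about fading. The lean towards a larger fall in sham does depend on fading: 61-90% with none of the benefit retained, 20-36% with half and 2.5% with all, under the assumptions listed. These figures show what is possible, not how likely it is. The baseline-to-intraoperative contrast, the stated 80.53% power and the sample size are unaffected. The risk is a misleading co-listed result, not a wrong trial conclusion.

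**What to change.** In Sections 2.1 and 6.2.1:
1. Make the Aim 1 test the between-arm comparison of the intraoperative score, adjusted for baseline pain. Baseline pain is already collected, and under the stated assumptions this comparison is at least as precise as the change score.
2. Make the between-arm comparison of the post-procedure score, also adjusted for baseline pain, the secondary comparison. Its sign can be read directly.
3. If the intraoperative-to-postoperative change is kept, report it descriptively as recovery beside the three time-specific means. Note that a smaller fall is expected in the active arm if a benefit fades, and do not use the change as evidence for or against efficacy.

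The cost is a wording change in two sections, with no new data, participants or visits. The downside is that one formal test of recovery is lost.

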Prior to 2017, we performed all cystoscopic Onabotulinum Toxin A injections in the operating room at Mayo Clinic in Rochester, Minnesota. Patients with refractory overactive bladder require repeat injections and had to return to the operating room on average every 6-7 months. This would be almost a whole day's ordeal for patients. In order to minimize the inconvenience to patients and to provide cost effective patient care, Cystoscopic Onabotulinum A injections were transitioned to the office setting in 2017.

For successful adoption of office cystoscopic Onabotulinum Toxin A injection, the procedure has to be an acceptable option to patients. As noted earlier, office cystoscopy in itself is an uncomfortable procedure and the addition bladder injections make it painful. The pain patients experience during the procedure can deter them from wanting a repeat cystoscopic injection in office setting. Currently we use local anesthesia (intra-urethral lidocaine), intra-vesicular lidocaine solution, distraction techniques (conversation/music/’squeeze balls’), and aromatherapy for pain control during this procedure. Despite this, a preliminary review of 91 office Cystoscopic Onabotulinum A injections performed at our institution from 2017 to 2019 showed that the average intra-procedural pain score was 5 on a numerical pain scale of 0 to 10.

Therefore, we chose the pain experienced during the office Cystoscopic Onabotulinum Toxin A injection and the patient’s satisfaction from the procedure as the specific aims for this study.

2 Study Objective(s)/Aims(s):

2.1 *Specific Aim #1: To assess whether the TENS units are effective for intraoperative pain management during office cystoscopic Intradetrusor Onabotulinumtoxin A in women with OAB.*

We plan to compare participant reported pain using a 0-10 numerical pain scale at baseline, during and after cystoscopic intradetrusor onabotulinumtoxin A injection in patients randomized to active TENS units and placebo TENS units. We will compare the change in numerical pain scale from baseline to intraoperatively and intraoperatively to postoperatively between both groups.

[figure not shown]
2.2 *Specific Aim #2: To evaluate the effect of TENS units on participant satisfaction following cystoscopic intradetrusor onabotulinumtoxin A injection in women with OAB.*

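### Aim 1 points to pain during the injection, but no section makes it the primary comparison, and one of its two change contrasts cannot serve as a success criterion

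*Combined protocol and SAP*

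**What the plan says.** Two places indicate what the investigators care about. Section 1.6 says that they chose pain during the injection as one of their aims, and reports from their own records that "the average intra-procedural pain score was 5 on a numerical pain scale of 0 to 10". The Aim 1 title in section 6.2.1 reads "To assess whether the TENS units is effective for intraoperative pain management".

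The operative sections are less definite:

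- **Section 3.5** lists three raw scores as primary endpoints without ranking them. The first is "Numeric Analog Pain Score (0-10) at Baseline before Office Cystoscopic Onabotulinum Toxin A injection"; the second is "collected during middle of the procedure, after the 10th injection"; the third is taken five to ten minutes after the procedure. No change score is listed.
- **Sections 2.1 and 6.2.1** promise two comparisons: "We will compare the change in numerical pain scale from baseline to intraoperatively and intraoperatively to postoperatively between both groups".
- **Section 6.2.1, Data Analysis**, says that a "random effect longitudinal model will be adjusted to the data controlling by treatment and selected covariates at baseline". It names no contrast and no arm-by-time term.
- **Section 6.2.1, Interpretation**, accepts the hypothesis on this condition: "Assuming that pain as measured is decreased in the Active TENS group when compared to the placebo TENS group". No time point is given.
- **Section 6.1** gives 80.53% power for 27 per arm, means of 4.0 and 2.0 and SDs of 2.0 and 3, "using a two-sided two-sample unequal-variance t-test". The means and SDs are described only as those of the pain scale.

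**The concern.** A reader of section 6.2.1 cannot tell which result decides Aim 1. That matters because the two listed changes need not agree. The mid-procedure score enters them with opposite signs, so a device that lowers pain during the injections improves the first contrast and, other things equal, worsens the second.

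The design leaves room for this. Under section 5.2, stimulation starts 5 minutes before the cystoscopy and stops with it, and the last score follows shortly afterwards, so the documents do not rule out a benefit that fades. An effective device could then give one Aim 1 result in its favour and one against it. The decision has consequences: if Aim 1 is not met, section 6.2.1 calls for subgroup and risk-factor analyses, and the review after 30 participants is to discuss efficacy.

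The power statement has the related problem that it belongs to no named comparison.

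**Working it through.** **1. The plan's own figure.** Inputs from section 6.1: n = 27 per arm, difference 2.0, SDs 2 and 3, two-sided alpha 0.05.

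- SE = sqrt(4/27 + 9/27) = sqrt(13/27) = 0.694
- Noncentrality = 2/0.694 = 2.88
- Satterthwaite df = 13² × 26/(4² + 9²) = 4394/97 = 45.3
- Noncentral-t power = 80.53%, as stated

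The arithmetic is right. With 10% dropout, 27/0.9 = 30 per arm, also as stated.

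**2. Does it carry over to the baseline-to-intraoperative change?** The documents give no SDs by time point and no within-person correlation, so these are assumed. Let 2 and 3 be the mid-procedure SDs, sb the baseline SD in both arms and r the correlation. The arm variances of the change are 4 + sb² - 4r·sb and 9 + sb² - 6r·sb. They sum to 13 + 2sb² - 10r·sb, against 13 for the powered test. The two are equal when r = sb/5. Power for a 2-point difference:

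| sb | r = 0 | 0.2 | 0.3 | 0.4 | 0.5 |
|---|---|---|---|---|---|
| 1 | 74.8% | 80.6% | 83.6% | 86.6% | 89.5% |
| 1.5 | 68.2% | 76.2% | 80.6% | 85.1% | 89.6% |
| 2 | 60.4% | 69.5% | 74.9% | 80.6% | 86.7% |

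For r between 0.2 and 0.5 the range is about 70-90%, and 9 of the 12 settings reach 80.53%.

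**3. What the second contrast measures.** This is algebra and needs no SD. Take the mid-procedure means as 4 (sham) and 2 (active), and let e be the postoperative benefit, sham mean minus active mean. Active minus sham in the change (post minus mid) equals (4 - 2) - e = 2 - e. A positive value means that pain fell less on active TENS, so it favours sham. The postoperative means below are examples.

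| Post mean, sham / active | e | Second contrast | Direction |
|---|---|---|---|
| 1 / 1 | 0 | (1-2) - (1-4) = +2 | sham |
| 2 / 1 | 1 | (1-2) - (2-4) = +1 | sham |
| 3 / 1 | 2 | (1-2) - (3-4) = 0 | neither |
| 3 / 0 | 3 | (0-2) - (3-4) = -1 | active |

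With equal baselines, the first contrast is -2, in favour of active, in every row.

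**4. How often the two would conflict (illustrative only).** Assumed: baseline SD 1, 1.5 or 2; post SD 1.5 or 2; correlation 0.2 to 0.5; 24 settings of 40,000 simulated trials, with a separate Welch test on each change.

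| | Benefit ends with the procedure (e = 0) | Half persists (e = 1) |
|---|---|---|
| Second contrast significant for sham | 69-90% | 23-37% |
| Both significant, in opposite directions | 57-85% | 22-36% |

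**5. A single baseline-adjusted mid-procedure comparison.** ANCOVA of the mid-procedure score on arm and baseline pain, under the same assumptions, has 81-89% power for r of 0.2-0.5, with type I error of 4.9-5.3%. At r = 0 it has 79.7-80.0%, where the change score has 60-75%.

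**The case against.** The strongest reply is that the focus is already stated. Section 1.6 records a deliberate choice of pain during the injection, the Aim 1 title repeats it, and the only preliminary score reported is intra-procedural. If the inputs to section 6.1 describe that score, the 80.53% holds as written. This largely stands: the plan has a focus, and the defect is that sections 2.1, 3.5 and 6.2.1 do not carry it through. That the two changes have equal standing is inferred from the absence of a ranking; the documents do not say so.

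The second change is also a legitimate description of recovery and can favour active TENS if benefit grows after the procedure. That stands too; the objection is only to using it to judge success.

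The simulated rates have limits. The SDs, correlations and persistence are assumed, and separate Welch tests replace the planned longitudinal model. A normal variable with mean 2 and SD 3 falls below zero about 25% of the time, which a 0-10 scale does not allow. The algebra in step 3 does not depend on any of this.

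A reader might also infer that the error rate is doubled. In the simulations, letting either contrast count gives 4.8-5.2% in the direction favouring active TENS, against about 2.5% for one. No section states such a rule, so the documents do not support the inference.

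**Conclusion.** The point holds as a gap between stated focus and specified analysis, and it should be fixed. No section names the comparison that decides Aim 1, the success rule has no time point, and one listed primary score precedes treatment. The intraoperative-to-postoperative change is not a valid success criterion, because its arm difference of 2 - e is null or favours sham unless benefit grows after the procedure. That conclusion needs only the plan's 2-point difference, taken to apply mid-procedure.

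A reader might infer that the trial is underpowered or that 80.53% is wrong. Neither follows. The figure reproduces, and the 70-90% range for the first change rests on assumed SDs and correlations. Nor do the documents show that benefit fades; they only leave it open, so the conflict rates show what could happen and are not forecasts.

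**What to change.** Amend sections 2.1, 3.5, 6.1 and 6.2.1 as follows.

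- Make the arm difference in the mid-procedure score (after the 10th injection), adjusted for baseline pain, the single primary contrast. Estimate it by ANCOVA, or as the matching arm-by-time contrast if the longitudinal model is kept.
- Treat baseline pain as a covariate and remove it from the endpoints.
- Make the postoperative score and the intraoperative-to-postoperative change secondary.
- Rewrite the success rule under Interpretation so that it refers to the primary contrast.
- State in section 6.1 that 80.53% is the power of the unadjusted mid-procedure comparison under the stated SDs. Add that baseline adjustment is expected to give about the same power or more: about 80% at zero correlation and 81-89% at 0.2-0.5, under assumed SDs.

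If outcome data by arm have already been seen, for instance at the 30-participant review, date the choice and disclose it. The cost is wording and one degree of freedom. The sample size of 60 stands and no new data are needed.
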